10.19.4 Worst Case Imputation

In order to assess the robustness of the primary efficacy analysis for selected key secondary endpoints, the worst case analysis will be used which will assign missing data in the active arm using the average of the observed values in the placebo arm at a visit. Likewise for missing values in the placebo arm, the average of the observed values in the active arm at a visit will be used. This analysis will only be considered meaningful if the results of the primary analysis for the key secondary endpoints are significant for C21.

The adjusted ordinal scale value will be used in this analysis and the average will be rounded to the nearest whole number prior to analysis. For the key secondary endpoint of oxygen supplemental free days, death will be given a value of -1, subjects with no post treatment data a value of 0 in the analysis.

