10.13 Number of Oxygen Free Days

Subjects will be considered oxygen free on a trial day if they do not have supplemental oxygen usage on that day. Supplemental oxygen usage is defined in Section 10.10 and subjects will be assessed for supplemental oxygen usage on each post treatment day up to trial Day 29 (i.e. from trial Day 2 to Day 29).

The number of oxygen free days for a subject will be the sum of the number of oxygen free days in hospital and number of oxygen free days at home if applicable. These days do not need to be consecutive. Missing data will be imputed as per Section 10.19.1.

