10.19 Missing Data

In general, missing safety data will not be imputed. However, safety assessments in the form of <x (i.e. below the lower limit of quantification) or >x (i.e. above the upper limit of quantification) will be imputed as x in the calculation of summary statistics but displayed as <x or >x in the listings. Missing FiO₂ values will be imputed as per Appendix 3.

In all efficacy analysis subjects who die will always be treated as the worst case following the date of death. For endpoints where multiple imputation will not be implemented, subjects who discontinue the trial early will be assessed in the analysis based on their last known status as discussed in Sections 10.15, 10.16 and 10.17. Other missing data will be imputed using multiple imputation as outlined below.

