10.19.1 Multiple Imputation

Missing ordinal scale data at scheduled time points will be imputed using multiple imputation. Multiple imputation relies on the assumption of data being missing at random (MAR) i.e. the missingness can be explained by the observed data and missing data does not depend on unobserved data after accounting for observed factors. Subjects will only have missing data imputed for post-baseline scheduled visits (Day 2 to Day 29, Day 60).

The following steps will be used to impute the missing data. Prior to the missing data imputation all observed 8-point ordinal scale data will be re-mapped per Table 3 to ensure discharged subjects with supplemental oxygen use are treated as clinically worse than discharged subjects with no oxygen use. This will also ensure information on at home oxygen use is explicitly contained in the ordinal scale score. The value of the adjusted 8-point ordinal scale to use in the analysis for all days following discharge will be assigned as per Section 10.10. On the day of discharge, the following rules will be used to assign a value of the adjusted ordinal scale:

- If a subject has a scheduled visit with an ordinal scale value other than 2, this value will be used in the analysis for the day of discharge.
- If a subject has a missing assessment or a value of 2 is recorded as the scheduled assessment, a subject will be assigned a value of 1 or 2 on the adjusted 8-point ordinal scale on the day of discharge as outlined in Section 10.10.

If a subject has an ordinal scale value of 8 at any visit or the subject has a date of death, records on or following date of death will be handled as follows in the analysis:

- All days following day of death will be set to 8.
- For the day of death, if the subject has a non-missing value on the ordinal scale that is not a value of 8 this will be the value used in the analysis.
- If a subject has a missing value on the day of death the value of 8 will be used.

Subjects who die will be removed from the Imputation in step 2. Only subjects who have not died will have their data imputed. Following the imputation, data for subjects who died will be included in all imputed datasets as observed.

A random seed of 2188 will be used for all imputation in this analysis.

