Subjects free of respiratory failure is defined as subject with an ordinal scale score of ≤ 5 at Day 15. A subject is considered a responder for this endpoint if they have a value of ≤ 5 at Day 15.

Treatment groups will be compared using a logistic regression model adjusting for treatment, baseline disease severity and region (as described in Appendix 2). Missing data due to trial withdrawals will be multiply imputed as per Section 10.19.1. Subjects who die prior to Day 15 will be considered non-responders in the analysis. The adjusted proportions as calculated from Ge et al., 2011 and the statistics (treatment difference, SE and CI) following multiple imputation will also be presented. The ITT will be used for the analysis. The number of responders/non-responders will also be presented (these will be the non-imputed values).

12.5.3.5 Subjects discharged and free of supplemental oxygen at Day 15

For this endpoint a subject will be considered a responder in the analysis if the subject has a score of ≤ 2 on the ordinal scale and they are free of supplemental oxygen use at Day 15. Refer to Section 10.10 for details on the classification of subjects as free of supplemental oxygen use at a visit.

Treatment groups will be compared using a logistic regression model adjusting for treatment, baseline disease severity and region (as described in Appendix 2). Missing data due to trial withdrawals will be multiply imputed as per Section 10.19.1. Subjects who die prior to Day 15 will be considered non-responders in the analysis. The adjusted proportions as calculated from Ge et al., 2011 and the statistics (treatment difference, SE and CI) following multiple imputation will also be presented. The ITT will be used for the analysis. The number of responders/non-responders will also be presented (these will be the non-imputed values).

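### The worst-case imputation in SAP 10.19.4 is in general only half of a worst case for the three key secondary endpoints that use it, and for oxygen-free days it can run in favour of C21

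*SAP*

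**What the plan says.** SAP 10.19.4 sets out one rule for missing scores. For C21 it will "assign missing data in the active arm using the average of the observed values in the placebo arm at a visit". For placebo the rule is mirrored: "Likewise for missing values in the placebo arm, the average of the observed values in the active arm at a visit will be used". It works on the adjusted ordinal scale, and "the average will be rounded to the nearest whole number prior to analysis". For oxygen-free days, death is scored -1 and "subjects with no post treatment data a value of 0 in the analysis", in either arm. The section regards the analysis as meaningful only when the main result for the endpoint is significant for C21.

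Section 12.5.3.6 and Appendix 1 list this as worst-case imputation for three key secondary endpoints: oxygen-free days to Day 29, freedom from respiratory failure at Day 15, and discharged and oxygen-free at Day 15.

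The cut-offs are set elsewhere in the SAP:
- Respiratory failure (12.5.3.4): "A subject is considered a responder for this endpoint if they have a value of" 5 or below.
- Discharged and oxygen-free (10.19.1, step 3): adjusted score exactly 1.
- Oxygen-free day (10.19.1, step 3): adjusted score 1, 3 or 4. Score 2 is discharge on home oxygen (10.8, Table 3) and does not count.

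On deaths, 10.19 says "In all efficacy analysis subjects who die will always be treated as the worst case following the date of death", and 10.19.1 adds "All days following day of death will be set to 8".

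**The concern.** For a treatment comparison, a worst case makes missing C21 outcomes unfavourable and missing placebo outcomes favourable. Exchanging arm means does pull the arms together on the raw score, but none of the three endpoints is the raw score. After rounding and cutting, both arms' missing subjects can land on the same side, so that one arm's half of the worst case is lost. Because the oxygen-free definition skips score 2, the direction can even reverse. A result that stays significant could then be reported as having survived a worst case that was not fully applied.

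**Working it through.** Section 10.19.4 states no figure to reproduce, so the check puts the rule through each endpoint definition. It is not stated whether deaths enter the observed averages; the bounds below allow scores up to 8, which is the case most favourable to the rule.

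**1. Free of respiratory failure (score 5 or less).** A missing C21 subject becomes a non-responder only if the placebo mean is at least 5.5.
- If a share g of observed placebo subjects score 5 or less, the mean is at most 5g + 8(1-g) = 8 - 3g. Reaching 5.5 needs g ≤ 2.5/3 = 83.3%.
- If a share f score 2 or less, the mean is at most 2f + 8(1-f) = 8 - 6f. Reaching 5.5 needs f ≤ 2.5/6 = 41.7%.

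Above either limit, every missing C21 subject is a responder. With the C21 mean also below 5.5, missing placebo subjects are responders too, and only the placebo half of a worst case is applied.

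**2. Discharged and oxygen-free (score 1).** A full worst case needs a C21 mean below 1.5 and a placebo mean of at least 1.5. If a share h of observed C21 subjects score 6 or more, the C21 mean is at least (1-h) + 6h = 1 + 5h, which is 1.5 or more once h ≥ 10%. If both means are at least 1.5, all missing subjects in both arms are non-responders and only the C21 half is applied.

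**3. Oxygen-free days (scores 1, 3, 4).** There are 8 × 9/2 = 36 rounded pairs with C21 no worse than placebo.
- Full worst case, 13: placebo 2 with C21 1, plus placebo 5 to 8 with C21 1, 3 or 4 (1 + 4 × 3).
- Reversed in favour of C21, 2: placebo 3 or 4 with C21 2.
- Same status in both arms, 36 - 13 - 2 = 21. If both scores count as free, the placebo half is applied; if neither does, the C21 half is.

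These are counts of pairs, not probabilities.

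**4. No post-treatment data.** Such subjects get 0 oxygen-free days in both arms. That is unfavourable for C21, as intended. For placebo, the worst case for the comparison would be all 28 days (Day 2 to Day 29, SAP 10.13).

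**5. Illustration.** The documents give no Day 15 score distributions, so the rates are assumed. There are 150 per arm, and 5% of 150 = 7.5 is taken as 8 missing, leaving 142 observed. The 5% is the withdrawal rate in SAP 8.1, which belongs to the Day 60 calculation. Tests are unadjusted Pearson chi-square.

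Observed counts are 128 and 114 free of respiratory failure (90% and 80% of 142), and 106 and 85 discharged and oxygen-free (75% and 60%). C21 then has 106 at score 1, 22 at 2 to 5 and 14 at 6 to 8, so its mean lies between 1.65 and 2.31 and rounds to 2. Placebo has 85, 29 and 28, so its mean lies between 2.19 and 3.20 and rounds to 2 or 3. Both Day 15 endpoints are therefore in the half-worst-case branch.

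| Endpoint | SAP rule, of 150 | True worst case, of 150 |
|---|---|---|
| Free of respiratory failure | 136 vs 122, +9.3 points, p=0.020 | 128 vs 122, +4.0, p=0.35 |
| Discharged and oxygen-free | 106 vs 85, +14.0, p=0.012 | 106 vs 93, +8.7, p=0.11 |

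At these rates the Day 15 pair (placebo, C21) for oxygen-free status is (2,2), half a worst case, or (3,2), reversed. That is one day of 28; the effect on the summed count was not quantified.

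**6. Sensitivity to the assumptions.**
- At 90/80 the true worst case stays significant with 1 or 2 missing per arm (p=0.025, 0.039) but not with 3 (p=0.081).
- At 75/60 it stays significant with up to 5 (109 vs 92, p=0.037), is borderline with 6 (p=0.050) and is not significant with 7 (p=0.086).
- For respiratory failure with 8 missing, over all 88 whole-percent pairs of 88-95% (C21) and 78-88% (placebo), the SAP rule is significant in 49 and the true worst case in 7. They disagree in 42.

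**The case against.** The strongest reply is that 10.19.3 already does the job. The tipping-point analysis covers the same three endpoints, runs whenever the endpoint's main result is significant, and reports the difference, interval and p-value at each shift. It can set all missing C21 subjects to non-responder and then raise the placebo arm. In the illustrations the C21 shift alone is enough. At 90/80, with 6 of 8 missing placebo subjects as responders, moving 4 of 8 missing C21 subjects to non-responder gives 132 vs 120, p=0.059. At 75/60, with 5 of 8 missing placebo subjects as responders, moving all 8 gives 106 vs 90, p=0.052. The fragility would be visible in the planned output. That stands, and it limits the consequence. It does not correct 10.19.4, which is listed separately and carries the worst-case name.

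It is also fair that the rule is stated openly, that the rates and missing counts above are assumed, and that the planned test is an adjusted logistic model rather than a chi-square, so borderline values carry little weight. Day 15 missingness may be lower than 5%, because the protocol's schedule of activities (section 1.3, note 4) requires that visit for everyone. For oxygen-free days, subjects enter at score 5 or 6, so early-day means could fall in full-worst-case pairs such as placebo 5 with C21 4.

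A reader might infer that for oxygen-free days the rule usually applies no worst case at all. The definitions do not support that: the 21 same-status pairs each apply one half, and only the 2 reversed pairs work against the stated purpose.

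**Conclusion.** The point holds as a minor one. The rule has the worst-case property only when the rounded means straddle the endpoint's cut in the right direction. That conclusion follows from the SAP's definitions and needs no assumed data. How much it matters depends on the score distributions and the number missing. At the assumed rates with 8 missing per arm, significance survives the SAP rule and is lost under a true worst case; with few missing, both agree.

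A reader might go further and infer that the key secondary results themselves are unsafe, or that the plan has no real stress test for missing data. Neither follows. This is a listed sensitivity analysis, neither alpha nor the primary result depends on it, and 10.19.3 can reach the true extreme for the same endpoints. What is wrong is the label and the claim of robustness it would support.

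**What to change.** In 10.19.4, impute on the endpoint rather than on the averaged score:
- Both Day 15 endpoints: missing C21 = non-responder, missing placebo = responder.
- Oxygen-free days: missing C21 days = not oxygen-free, missing placebo days = oxygen-free, including placebo subjects with no post-treatment data.
- Keep the existing death rules (non-responder; -1 day).

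At minimum, rename the present rule, for example cross-arm mean imputation, in 10.19.4, 12.5.3.6 and Appendix 1, and do not report it as a worst case.

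Renaming costs wording only. The endpoint-level rule needs SAP wording and simple programming. Its drawbacks are that the result may look less favourable to C21 and that it overlaps with the end of the tipping-point sequence.

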11.0 Interim Analyses

No formal interim analysis will be performed in the study. The DMC will review the safety results after the first 150 randomized subjects have completed study up to Day 15.

12.0 Statistical Methods

All statistical analyses will use SAS® version 9.4 or higher. Unless otherwise noted, categorical variables will be summarized using counts and percentages. Percentages will be rounded to one decimal place, except 100% which will be displayed without any decimal places and percentages will not be displayed for zero counts.

Continuous variables will be summarized using the number of observations (n), mean, Standard Deviation (SD), median, Q1, Q3, minimum and maximum. The minimum and maximum values will be displayed to the same level of precision as the raw data, the mean, median, Q1, and Q3 to a further decimal place and the SD to two additional decimal places. The maximum number of decimal places will be 4, unless otherwise noted. P-values will be presented to 3 decimal places, with values less than 0.001 presented as <0.001.

In general, all data summaries will be presented by treatment group and overall. Efficacy outputs will not have an overall column. If not stated otherwise, p-values from statistical tests will be two-sided and CIs will be calculated using a 95% CI.

Stratification will be done based on baseline disease severity, that is the score on the ordinal scale at baseline (5 or 6), and region (North America, South and Central America, Europe, Asia, Africa). The actual stratification will be used as factors in the statistical analysis, subjects included in wrong stratum at randomization will be moved to their correct strata belonging in the analyses. Small stratum may be pooled in the analysis. Any pooling of stratum will be agreed prior to unblinding of the database. Region will be pooled as Europe vs the rest of the world (North America, South and Central America, Asia, Africa). For all models where region is a factor (including in the imputation), pooled region will be used. In the text of this document, region will mean pooled region. Factors may be removed from models if the factor is causing an issue with convergence. For subgroup analysis, factors that are aligned with the strata division will be deleted from the model.

Missing data will be handled as described in Section 10.19. The ITT is used to analyze endpoints related to the efficacy objectives, the PP will be used for sensitivity analyses related to efficacy objectives and the SS is used to analyze the endpoints and assessments related to safety. PK analyses will be presented using the PKS.

The statistical comparisons for the primary efficacy endpoint and the key secondary endpoints will be carried out in hierarchical order as below:

1. All-cause mortality up to Day 60
2. Time to sustained hospital discharge up to Day 60
3. Supplemental oxygen free days up to Day 29
4. Proportion of subjects free of respiratory failure at Day 15

5. Proportion of subjects discharged from hospital and free of supplemental oxygen at Day 15

This means that statistically significant results for the comparison in the higher rank are required to initiate the testing of the next comparison in the lower rank. All analysis will be performed in the above order, however if a statistical comparison is non-significant then all subsequent statistical analysis will be exploratory in nature and no formal conclusions will be drawn. In other words, if the test for endpoint 3 in the above order is non-significant, then endpoints 4 and 5 will be exploratory in nature.

Since a step-down procedure is used, each comparison will be tested at a significance level of 0.05 and an overall alpha level of 0.05 will be preserved.

All data collected during this trial regarding subject characteristics, efficacy and safety will be listed, unless otherwise specified. Screen failures will be excluded from all listings and tables if not otherwise noted. Listings will not show imputed data but will present data as reported.

12.1 Subject Disposition

The number of subjects screened, and the number and percentage of screen failure subjects, together with the reason for screen failure will be presented.

The number and percentage of subjects randomized, not treated and treated in the trial will be presented, with the number and percentage of subjects who prematurely withdrew from the treatment, withdrew from treatment but completed the trial, prematurely withdrew from the trial and a breakdown of the corresponding reasons for treatment and trial withdrawal.

Tabulations of the number and percentage of subjects included in each analysis set. A tabulation of subjects still in the trial at each post-baseline time point will be provided.

Subjects disposition will be listed for all randomized subjects.

12.2 Demographic and Baseline Characteristics

Demographic information and baseline characteristics will be summarized for the ITT, SS, and PP. Additionally, a summary of demographic characteristics by actual baseline severity strata will be presented for the ITT.

Descriptive statistics will be provided for

- Sex (Female, Male)
- Race (American Indian or Alaska Native, Asian, Black or African American, Native Hawaiian or Other Pacific Islander, White, Other, Not Reported, Unknown)
- Ethnicity (Hispanic or Latino, Not Hispanic or Latino, Not Reported, Unknown)
- Country
- Actual Region (North America, South and Central America, Europe, Asia, Africa) [Randomized region will be presented if any difference between actual region and randomized]
- Age (years) at informed consent (as collected on the Demographics CRF page),
- Age group (< 65 years, ≥ 65 years)
- Baseline body weight, height, and BMI. BMI will be derived as Weight (in kg)/Height (in m)²
- Actual Baseline Disease Severity strata (ordinal score 5 or 6 at baseline based on actual value and not randomized)
- Randomized Baseline Disease Severity strata (ordinal score 5 or 6 at baseline based on value used in randomization)

- Presence of Risk factors for Severe COVID-19 (subjects with any medical history preferred terms selected as a risk factor as defined by the investigator on the Medical history page of the CRF will be counted as Yes otherwise subjects will be counted as No)
- Number of Risk Factors (count of unique medical history preferred terms selected as risk factor for severe COVID-19 by the investigator)
- SARS-CoV-2 Variant

A listing for demographics will be provided for ITT.

Medical history conditions will be coded using Medical Dictionary for Regulatory Activities (MedDRA) version 24.0 or later. The number and percentage of subjects with each medical history term will be summarized by the MedDRA system organ class (SOC) and preferred term (PT) using the ITT. A listing for medical history presented for the ITT. Additionally medical history indicated by the investigator on the CRF as a risk factor for severe COVID-19 will be summarized by SOC and PT in the ITT.

COVID-19 diagnosis and history will also be summarized for ITT with descriptive statistics presented for the following:

- History of previous COVID-19 infections (Yes, No)
- Time since onset of current COVID-19 signs and symptoms calculated as:

Time since onset (days) = Start date of treatment – date of onset

- Time since current COVID-19 diagnosis

Time since diagnosis (days) = Start date of treatment – date of diagnosis

- Duration of current hospitalization calculated as:

Duration (days) = Start date of treatment – Start date of hospitalization

The start date of hospitalization is the start date for records indicated as Initial hospitalization on the COVID-19 Hospitalizations CRF page. Additionally the following categories for duration of current hospitalization in days will be presented :0, 1, 2, 3, 4, 5 days.

- Type of Oxygen Supplementation for current infection at baseline (Low flow oxygen device, High flow oxygen device, non-invasive mechanical ventilation). All types of oxygen supplementation will be presented even if not specifically specified in this list.

Information on COVID-19 diagnosis and history will also be listed for the ITT.

12.3 Treatments

12.3.1 Extent of Trial Drug Exposure

For the IMP, summary statistics will be provided for SS for duration of exposure, total number of dose administrated and total cumulative dose in the treatment period. The number and percentage of subjects who experience at least one overdose on any day during the treatment period will be provided. Any dose of C21 exceeding a total daily dose of 200 mg (i.e., 4 capsules of IMP) is considered an overdose.

The total cumulative dose will be calculated as:

Cumulative dose (mg) = 50x (Number of Capsules dispensed [56] – Capsules returned)

The total number of doses administered will be the difference between the number of capsules dispensed [56] and number of capsules returned. If returned amount is missing and the subject is indicated to have completed treatment, they will be treated as taking all capsules. If the subject discontinues treatment and

returned amount is missing, they will be treated as taking capsules as planned up to the day of discontinuation derived as:

$$\text{Cumulative dose (mg)} = 50 * (4 * (\text{duration of exposure}))$$

where duration of exposure for this calculation will be set to a minimum of duration of exposure and 14 days.

If first dose for subject that discontinues treatment and has no returned amount is in the evening (p.m.) the calculation will be as follows:

$$\text{Cumulative dose (mg)} = 50 * (2 + 4 * (\text{duration of treatment} - 1))$$

For these subjects with first dose in the p.m., if duration of exposure is >14 indicating the subject took the full treatment course, the cumulative dose will be assumed to be 56.

The duration of exposure will be derived as:

$$\text{Duration} = (\text{Last dose of IMP} - \text{First dose of IMP}) + 1$$

Duration of exposure will be summarized overall, by subjects whose first dose was in the morning and by subjects whose first dose was an evening dose. Duration of exposure will also be summarized by duration categories, the number of subjects exposed for 1-6 days, 7-13 days and 14+ days.

Overall compliance will be calculated as follows:

$$\text{Treatment Compliance (\%)} = 100 * \frac{\text{Total Number of Doses administered}}{\text{Expected Number of Capsules}}$$

For subjects who completed treatment, expected number of capsules will be 56. For subjects who discontinue treatment:

$$\text{Expected Number of Capsules} = 4 * \text{Duration of exposure}$$

Compliance will be summarized using the following categories: <80%, 80-90%, >90%.

The percentage of doses taken in hospital will be presented and derived as follows:

$$\% \text{ of Doses taken} = 100 * \frac{56 - \text{Number of Capsules dispensed on discharge}}{\text{Cumulative dose (total capsules taken)}}$$

For subjects who do not discharge during the treatment period or who discontinue the study prior to discharge from hospital during the treatment period, the % doses taken will be 100%.

The number of doses missed and reason dose missed will be summarized for subjects (this information will only be collected during the hospitalized period). Trial drug exposure will be listed. Drug accountability will also be listed.

